8.4. Recording of Adverse Events

All AEs encountered during the clinical study will be recorded in detail in the source documents and documented in the eCRF, from signature of the ICF through study exit. All AEs that meet the seriousness criteria (Section 8.6) should also be recorded on the SAE Report Form. All SAEs must be reported to the sponsor or delegated organization within the timeline stated in Section 8.7.

The recording of AEs will be based on data obtained from the following sources:

- Medical and surgical history
- Physical examinations including vital signs
- Clinical laboratory test results
- Information provided by the patient, either during the follow-up visits or in the patient's diary All clinical events, including both observed (such as any reaction at sites of application) and volunteered problems, complaints, or symptoms, are to be recorded. The need to capture this information is not dependent upon whether the clinical event is associated with the use of any IMP.

If at any time during the study a patient develops symptoms suggesting clinically significant bacteremia that can be attributed to *L. lactis* sAGX0407 (as determined by three consecutive positive blood cultures), study treatment will be discontinued.

A disposition plan for the management of clinical sepsis is provided in Appendix B.

Confidentiality Statement

For the purposes of this study, hypoglycemia events classified as level 1 as defined in Section 8.2.1 will not be recorded separately on the hypoglycemia event eCRF, unless the investigator feels that the event is medically important. Hypoglycemia events level 2 and 3 as defined in Section 8.2.1 will be recorded separately on the hypoglycemia event eCRF. The evaluation that produced the value or result should be repeated until that value or result returns to normal or can be explained and the participant's safety is not at risk. In addition, all hypoglycemia events meeting the definition of SAE as mentioned in Section 8.6, should be recorded as serious adverse events in the eCRF.

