8.9. Regulatory Reporting of Adverse Events

If there are serious, unexpected adverse drug reactions (for Europe, SUSAR: Suspected Unexpected Serious Adverse Reaction) associated with the use of the IMP, the appropriate regulatory agency(ies) and all participating investigators will be notified by the Sponsor or its designee in accordance with the following Guidance for Industry: Clinical Safety Data Management: Definitions and Standards for Expedited Reporting (ICH-E2A), Detailed Guidance on the Collection, Verification and Presentation of Adverse Event/Reaction Reports Arising from Clinical Trials on Medicinal Products for Human Use (CT-3).

It is the responsibility of the investigator to promptly notify the IRB/IEC of all unexpected serious adverse drug reactions involving risk to human patients. An unexpected event is one that is not reported in the current Investigator's Brochure of AG019 or teplizumab.

8.10.Expected adverse events

8.10.1AG019

As AG019 has not been studied in humans, there are no expected adverse events associated with AG019. However, due to the general profile of the IMP, sepsis as a result of systemic exposure of AG019 could be expected. Instructions on the management of clinical sepsis attributable to AG019 are described in Appendix B.

All SAEs which are reported, for which a relationship to AG019 cannot be excluded, will be reported as SUSARs (see Section 8.9).

Confidentiality Statement

8.10.2Teplizumab

A full description of the adverse events experienced by patients in trials using teplizumab is in the Investigator's Brochure. The descriptions below highlight the most common drug related events and potential adverse events.

XXX

Confidentiality Statement

Precigen ActoBio T1D, LLC	Clinical Study Protocol AG019-T1D-101

Confidentiality Statement

Precigen ActoBio T1D, LLC	Clinical Study Protocol AG019-T1D-101

Confidentiality Statement

10.STATISTICAL METHODS

Statistical considerations are briefly described below.

Descriptive statistical methods will be used to summarize the data from this study. Unless stated otherwise, the term descriptive statistics refers to number of patients (n), mean, median, standard deviation (SD), standard error of the mean (SEM), minimum and maximum for continuous data and frequencies and percentages for categorical data. The term "treatment group" refers to assigned dose group/dosing frequency.

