11.4.3.1 Criteria for premature study termination

If clinical sepsis occurs in a patient, and it is exclusively attributable to AG019 bacteria alone (confirmed by positive plating and PCR), the study will be terminated. Details about the evaluation and management of clinical sepsis of any kind (attributable to AG019 or not) are outlined in Appendix B.

11.4.3.2Criteria for suspension of enrollment

Enrollment (defined as initiation of treatment in a new patient) in all ongoing and planned study cohorts may be temporarily suspended if one of the following occurs:

XXX

In the event that these criteria are met, the DSMB will be notified in writing within 24 hours. The notification will include detailed information of the event(s) and finding(s) that have led to meeting the criteria for enrollment suspension. The DSMB will determine whether enrollment needs to be suspended until a safety review has been performed, and will notify the Sponsor of their decision in writing.

Confidentiality Statement

- If the DSMB concludes upon initial notification that enrollment should be suspended until a more detailed safety review has been performed, the Sponsor will inform the Institutional Review Boards/Ethics Committees/Research Ethics Board (IRB/EC/REB), FDA and other applicable regulatory authorities and all participating sites within 24 hours of the DSMB's decision and will schedule an ad-hoc DSMB meeting to review the relevant safety information. The safety review will include a comprehensive evaluation of the safety experience from this trial. A report of the safety review will be provided to the FDA, other applicable regulatory authorities, Institutional Review Boards/Ethics Committees/Research Ethics Boards (IRB/EC/REB) and all participating sites. Enrollment will not resume until a satisfactory report of the safety review has been provided by the DSMB.
- If the DSMB concludes that enrollment should not be suspended, the Sponsor may schedule an ad-hoc DSMB meeting to review the relevant safety information upon request of the DSMB.

*XXX

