11.4.3.3 Criteria for adjusting AG019 treatment

If clinically significant safety concerns relating to AG019 are identified in ≥ 20% of all patients treated with the high dose of AG019, the DSMB will recommend lowering the AG019 dose in all AG019 and Combination cohorts.

11.4.3.4Criteria for discontinuation of AG019 treatment in a single patient

If at any time during the study a patient develops symptoms suggesting clinically significant sepsis for any reason (as determined by 1 positive blood culture), study treatment (both AG019 and teplizumab as applicable) will be discontinued. In addition, the guidelines for management of clinical sepsis as outlined in Appendix B should be followed.

In addition, withdrawal of informed consent will result in discontinuation of AG019 treatment.

Pregnancy in a study participant, or in the female partner of a male participant, occurring after signature of the ICF must be reported within 1 calendar day after the Investigator has gained knowledge of them. The patient (if female) will discontinue IMP. Details of the outcome of the pregnancy (e.g. full term delivery, stillbirth, congenital anomaly, miscarriage) will be collected and reported no longer than one month after the expected due date. Any abnormal outcome in the neonate will be followed up.

Confidentiality Statement

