11.4.3.5.1 Temporary interruption of teplizumab infusions

If any of the following lab abnormalities is observed (normal range per local lab reference ranges), the test may be repeated on the same day. If the repeated test result normalizes, that day's dose may be given. If the value is still in the indicated range or worsens, or if the test cannot be repeated on the same day, that day's dose should be withheld.

XXX

If the above event(s) resolve(s) within 2 days, study drug dosing may be resumed according to the original schedule. The treatment course will not be extended beyond 12 days.

If the above events do not resolve after 2 consecutive days of interruption, the Medical Monitor must be consulted regarding continuation of study drug dosing.

11.4.3.5.2Permanent discontinuation of teplizumab infusions

The following situations, laboratory abnormalities, or adverse events will lead to permanent discontinuation of infusions *during the treatment course*: (Note: Day 1 is the first day of infusion)

XXX

Confidentiality Statement

11.4.3.6Further Evaluation after Withholding Teplizumab Infusions

The following are minimal assessments to be performed for those participants in whom an infusion is withheld (as described above):

XXX

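### Protocol 8.4 sets three positive blood cultures, and 11.4.3.4 sets one, for stopping study treatment in a symptomatic patient with L. lactis in the blood; nothing in the supplied text reconciles the two

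*Protocol*

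**What the plan says.** **Protocol 8.4 (Recording of Adverse Events).** The trigger is symptoms pointing to clinically significant bacteremia that can be attributed to L. lactis sAGX0407. The test and action are: "as determined by three consecutive positive blood cultures), study treatment will be discontinued". The section then refers the site elsewhere for management: "A disposition plan for the management of clinical sepsis is provided in Appendix B".

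**Protocol 11.4.3.4 (Criteria for discontinuation of AG019 treatment in a single patient).** The trigger is symptoms pointing to clinically significant sepsis, with no restriction on organism: "sepsis for any reason (as determined by 1 positive blood culture), study treatment (both AG019 and teplizumab as applicable) will be discontinued". The next sentence reads: "In addition, the guidelines for management of clinical sepsis as outlined in Appendix B should be followed".

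**Related text.**
- Protocol 4.5 lists sepsis of whatever cause among the reasons for which a patient may be removed, and gives no culture count.
- Protocol 11.4.3.1 ends the whole study if sepsis occurs and "it is exclusively attributable to AG019 bacteria alone (confirmed by positive plating and PCR), the study will be terminated". It adds: "Details about the evaluation and management of clinical sepsis of any kind (attributable to AG019 or not) are outlined in Appendix B".
- Protocol 8.10.1 says that no adverse events are expected with AG019, since it has not been given to humans, but then states that "due to the general profile of the IMP, sepsis as a result of systemic exposure of AG019 could be expected".
- The SAP contains no blood-culture rule.

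**The concern.** Both sections start from a symptomatic patient and end in the same action, stopping study treatment. They differ in the microbiological evidence required: three consecutive positive cultures against one. The higher count applies to the case where the organism in the blood is the product being given, and no reason is stated for that.

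At stake is how promptly a live, genetically modified organism is withdrawn from a symptomatic adult or adolescent in a first-in-human study. An investigator handling a suspected L. lactis bacteremia may reasonably look for the rule that names the organism. That rule is in 8.4. An investigator who acts on it alone might wait for two more cultures while dosing continues, although 11.4.3.4 already requires dosing to stop.

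**Working it through.** There is no figure in the plan to reproduce, so the check sets the texts side by side.

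**1. The two rules**

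| | Protocol 8.4 | Protocol 11.4.3.4 |
|---|---|---|
| Clinical trigger | Symptoms of significant bacteremia | Symptoms of significant sepsis |
| Cause | Attributable to L. lactis sAGX0407 | Any |
| Culture evidence | 3 consecutive positive | 1 positive |
| Action | Stop study treatment | Stop AG019 and, where given, teplizumab |
| Refers to the other section? | No | No |
| Refers to Appendix B? | Yes | Yes |

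**2. Do they overlap?** The supplied text defines neither bacteremia nor sepsis. Section 11.4.3.4 recognises sepsis by symptoms plus one positive culture, from any cause. A symptomatic patient whose blood grows L. lactis therefore falls within it. Section 8.4 moves directly from its bacteremia rule to the plan for managing sepsis, so it treats the two as one clinical pathway.

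**3. Apply both rules to that patient**

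| Culture results so far | 8.4 requires stopping? | 11.4.3.4 requires stopping? |
|---|---|---|
| Positive | Not yet | Yes |
| Positive, positive | Not yet | Yes |
| Positive, negative, positive | Not yet (not consecutive) | Yes, since the first |
| Positive, positive, positive | Yes | Yes, since the first |

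The difference is 3 − 1 = 2 further positive cultures, and more if a negative result breaks the run.

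**4. Can the difference be turned into time or events?** No. The supplied text gives no interval between cultures and no sepsis rate. Protocol 5.1.1 (Table 2) gives only the exposure per day of waiting: 2 capsules at the low dose or 6 at the high dose. In the combination cohorts there is also up to one teplizumab infusion per day if the event falls within the first 12 days.

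**5. Does any other visible text settle the count?**
- 4.5 permits removal but does not require it, and gives no count.
- 11.4.3.1 is a study-level rule with a different attribution test (plating and PCR).
- 11.4.3.5.2 introduces its list with "The following situations, laboratory abnormalities, or adverse events will lead to permanent discontinuation of infusions". The list is redacted, and it concerns infusions, not capsules.
- Appendix B is cited in 8.4, 8.10.1, 11.4.3.1 and 11.4.3.4 but is not in the supplied text. In 11.4.3.4 it applies on top of stopping, so the one-culture stop does not wait for it. Section 8.4 has no equivalent wording.

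**The case against.** The strongest reply is that the rules can both be obeyed. Each says when treatment must stop, and neither says that it may continue. Section 8.4 does not make three cultures a precondition for stopping. A site that stops at one positive culture breaches nothing, while a site that waits for three in a patient who meets 11.4.3.4 breaches 11.4.3.4. That section is broader and stricter, and it sits under the stopping criteria, whereas 8.4 is about recording adverse events. Section 4.5 also lets the investigator withdraw a patient without waiting for any culture. All of this stands. A reader might infer from the differing counts that the protocol contradicts itself, or that it authorises dosing until a third positive culture. The text supports neither reading.

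A second reply is that three cultures may be meant to attribute the event to AG019, since the parenthesis follows directly on the attribution wording. That is possible. But the sentence ends in stopping treatment, and 11.4.3.1 attributes sepsis to AG019 by another test. If attribution is the purpose, 8.4 does not say so.

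A third reply is that Appendix B may reconcile the counts. It may, so the lack of a reconciling rule is established only for the supplied text. Its absence there should not be read as a gap in the plan. Even if Appendix B is clear, 8.4 would still give three where 11.4.3.4 gives one.

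Finally, the sepsis risk in 8.10.1 is a theoretical one drawn from the product's profile, not an observed rate. That limits how heavily the point can be pressed.

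**Conclusion.** The point holds as an inconsistent patient-safety threshold. Section 8.4 is wrong as written: applied alone, it would leave a symptomatic patient on a live product after 11.4.3.4 has required stopping. The size is two positive cultures, with no computable delay and no computable number of events. A count of patients to whom the rules apply would not measure the harm.

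The conclusion assumes that symptomatic L. lactis bacteremia falls within sepsis for any reason in 11.4.3.4, as that section's own test implies, and that some sites may consult 8.4 without 11.4.3.4. Many would stop at the first positive culture in any case.

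A reader might infer some effect on the trial's results. The documents do not support that: the primary endpoint is the incidence of treatment-emergent adverse events, the study is descriptive, and no endpoint, sample size or error rate depends on this rule.

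**What to change.** Amend the sentence in Protocol 8.4 in one of two ways:

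- Replace the three-culture criterion with the rule in 11.4.3.4: stop AG019, and teplizumab where applicable, on one positive culture in a symptomatic patient.
- Delete the criterion and cross-refer to 11.4.3.4.

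If three consecutive cultures are meant only to attribute the event to AG019, say so. State in the same sentence that treatment stops at the first positive culture, and explain how the count relates to the plating and PCR test in 11.4.3.1. In either case, check that Appendix B uses the same count.

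The cost is one amended sentence and one check, with no added data collection. The downside is an occasional stop on a contaminated culture, which 11.4.3.4 already accepts.

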8.5. Adverse Event Follow-up Period

All patients with AEs will be followed until the event resolves, stabilizes, becomes chronic, the patient completes the study or the patient is lost to follow-up.

8.6.Serious Adverse Event Definition

In addition to classifying the AE as mild, moderate, severe, life-threatening or fatal, the Investigator should determine whether or not an AE is an SAE. The Investigator shall make an accurate and adequate report on any SAE to the Sponsor or its designee and to any IRB/IEC that has reviewed and is continuing to review the study regarding any SAEs (see Sections 8.7 and 8.9).

An SAE is defined as any AE occurring at any dose regardless of relationship to IMP that results in any of the following outcomes:

- results in death,
- is life-threatening, NOTE: The term "life-threatening" in the definition of "serious" refers to an event in which the patient was at risk of death at the time of the event; it does not refer to an event which hypothetically might have caused death if it were more severe.
- requires inpatient hospitalization or prolongation of existing hospitalization,
- results in persistent or significant disability/incapacity, or
- is a congenital anomaly/birth defect.

Medical and scientific judgement should be exercised in deciding whether expedited reporting is appropriate in other situations, such as important medical events that may not be immediately lifethreatening or result in death or hospitalization but may jeopardize the patient or may require intervention to prevent one of the other outcomes listed in the definition above. These should also usually be considered serious. Examples of such events are intensive treatment in an emergency room or at home for allergic bronchospasm; blood dyscrasias or convulsions that do not result in hospitalization; or development of drug dependency or drug abuse.

The following situations will be considered important medical events and must be reported as SAEs:

Confidentiality Statement

- 1. Grade 4 or higher lymphopenia for 7 or more days occurring in the first 30 days after the start of the teplizumab infusion.
- 2. Grade 3 or higher lymphopenia occurring anytime later than the first 30 days after the start of the teplizumab infusion.

Complications that occur during hospitalization are AEs. If a complication prolongs hospitalization, the event causing the prolongation is an SAE. Planned hospitalizations are not considered SAEs.

"Inpatient hospitalization" means the patient has been formally admitted to a hospital for medical reasons. This may or may not be overnight. It does not include presentation at an emergency department.

Pregnancy in a study participant, or in the female partner of a male participant, occurring after signature of the ICF are considered immediately reportable events using specific reporting forms and must be reported within 1 calendar day after the Investigator has gained knowledge of them. The patient (if female) will discontinue IMP. Details of the outcome of the pregnancy (e.g. full term delivery, stillbirth, congenital anomaly, miscarriage) will be collected and reported no longer than one month after the expected due date. Any abnormal outcome in the neonate will be followed-up.

8.7. Reporting of Serious Adverse Events

For any SAEs, regardless of causal relationship, the Investigator must inform the Sponsor's pharmacovigilance vendor (XXX), the contract research organization (CRO) Project manager or Lead clinical research associate (CRA) as well as the Sponsor's representatives mentioned on the Contact Details page of this protocol within 1 calendar day of becoming aware of the event by mailing the completed SAE Report Form and any other pertinent SAE information to XXX as indicated on the SAE Report Form. Follow-up information collected for an initial report of an SAE must be reported to XXX within 1 calendar day of receipt by the Investigator.

XXX

Reports of any pregnancy in a patient, or partner of a patient, must also be emailed to the above mentioned email address within 1 calendar day (see Section 8.6).

The information to be recorded for SAEs should include the following:

- The onset of any new AE or the worsening of an observation documented from signature of the ICF
- The specific type of event in standard medical terminology
- The duration of the clinical event (start and stop dates)
- The severity of the clinical event
- Seriousness (SAE) criteria
- Relevant laboratory and examination results
- Dosing schedule of IMP(s)

Confidentiality Statement

- Indications and dosing schedules of concomitant medications
- Relationship of the AE to the IMP(s) as defined in Section 8.3
- Management of IMP(s) administration and other action taken to alleviate the clinical events
- Past medical and surgical history and concurrent diseases
- De-challenge/re-challenge results, if applicable
- The outcome of the clinical event
- Serious Adverse Event Recording Period

SAEs will be collected and recorded by the Investigator beginning from the signature of the ICF until the patient is withdrawn or has completed the study.

